Cerebrolysin as an Early Add-on to Reperfusion Therapy: Risk of Hemorrhagic Transformation after Ischemic Stroke (CEREHETIS). A Prospective, Randomized, Active-Control, Multicenter Pilot Study

Statistical Analysis Plan

Date of issue: 01 December 2020 (study's original report)

Editing:

- 01 May 2023: Added SAP for post hoc analysis (heterogeneous treatment effect analysis)
- 25 April 2024: Added SAP for secondary analysis (survival analysis)

I. Statistical Analysis Plan (Original Study)

1. Introduction

The CEREHETIS trial is a prospective, randomized, multicenter study designed to evaluate the efficacy and safety of Cerebrolysin as an adjunct to reperfusion therapy in patients with acute ischemic stroke (AIS). Hemorrhagic transformation (HT) remains a serious complication of intravenous thrombolysis (IVT) in AIS, contributing significantly to poststroke morbidity and mortality. Cerebrolysin, a neuroprotective agent, has shown promise in preclinical studies for its potential to reduce blood-brain barrier permeability and mitigate neuroinflammation. This study aims to determine whether the addition of Cerebrolysin to standard IVT can reduce the incidence of HT and improve neurological recovery and functional outcomes in stroke patients.

The primary outcome focuses on the rate of any HT and symptomatic HT within 14 days post-intervention, while secondary outcomes include assessments of safety, neurological recovery, and long-term functional status. Advanced imaging analyses, including diffusion-tensor imaging (DTI) and computed tomography (CT) perfusion, will provide further insights into the impact of Cerebrolysin on brain recovery.

2. Objective and Endpoints

- **Primary Objective**: To assess whether Cerebrolysin reduces the incidence of any and symptomatic hemorrhagic transformation (HT) within 14 days in AIS patients undergoing IVT.
- Secondary Objectives:
 - To evaluate neurological recovery using the National Institutes of Health Stroke Scale (NIHSS) at day 1 and day 14.
 - To assess long-term functional outcomes using the modified Rankin Scale (mRS) at day 90.
 - To assess the safety of Cerebrolysin in combination with IVT by evaluating adverse event (AE) rates.
 - To explore changes in advanced imaging parameters, specifically DTI and CT perfusion metrics, as markers of Cerebrolysin's effect on blood-brain barrier integrity and infarct recovery.

3. Trial Design

The CEREHETIS trial is a prospective, randomized, open-label, multicenter, parallel-group, phase IIIb pilot study with an active control. Patients are randomized in a 1:2 ratio to receive either IVT alone or IVT with Cerebrolysin.

4. Sample Size Calculation

- **Primary Endpoint (HT Rate)**: Based on the assumption that 20% of control group patients will experience HT, with a target odds ratio (OR) of 0.5 in the Cerebrolysin group.
- Significance Level: 0.05
- **Power**: 80%
- Dropout Rate: 10%
- **Design:** 1:2 allocation ratio between the intervention and control groups to optimize power efficiency and minimize required sample size for this pilot study.

5. Randomization and Blinding

- **Randomization**: Simple randomization across centers using Bernoulli variates (probability parameter of 0.333), with sealed opaque envelopes for treatment allocation.
- **Blinding**: Due to the distinct yellow color of Cerebrolysin, treatment blinding was not feasible; however, imaging analyses are blinded.

6. Data Collection and Time Points

Data collection occurs at the following time points:

- Baseline (Day 0): Demographic data, NIHSS, CT, DTI baseline imaging
- Day 1: Follow-up imaging and NIHSS assessment
- Day 7 and Day 14: NIHSS score, follow-up CT, and DTI imaging on day 14
- Day 90: Modified Rankin Scale (mRS) assessment for functional outcome

7. Statistical Analysis

a. Descriptive Statistics

- **Continuous Variables**: Presented as median (M) and interquartile range (IQR) due to non-normal distributions.
- **Categorical Variables**: Presented as percentages and analyzed with χ^2 -tests.

b. Comparative Analysis

- Primary Analysis (HT Rates):
 - Comparison of HT Rates: Logistic regression will compare the rates of any and symptomatic HT between the Cerebrolysin and control groups. Odds ratios (OR) with 95% confidence intervals (CI) will be reported.
 - Adjustment for Confounders: Age, NIHSS, ASPECTS score, and baseline variables such as history of hypertension and previous stroke will be included in multivariate models to control for potential confounding.
- Secondary Analysis:
 - **Neurological Recovery (NIHSS)**: The Mann–Whitney U test will compare NIHSS scores between groups at day 1 and day 14.
 - **Functional Outcome (mRS)**: The mRS scores on day 90 will be assessed using a χ^2 -test for favorable outcomes (mRS ≤ 2). Additionally, a shift analysis will be conducted to evaluate distributional differences in mRS scores between groups.

c. Advanced Imaging Analysis (Exploratory)

- Evaluate DTI and CT perfusion parameters in middle cerebral artery (MCA) stroke patients, focusing on markers such as fractional anisotropy, axial, radial, and mean diffusivity, and permeability–surface area product (PS).
- Statistical Methods:
 - **Group Comparisons**: The Mann–Whitney U test will be used to compare continuous imaging metrics between the Cerebrolysin and control groups at each time point (day 1 and day 14).
 - Laterality Index Analysis: Calculate the laterality index to assess asymmetry in imaging metrics between the affected and contralateral sides, with paired t-tests or Wilcoxon signed-rank tests for within-group comparisons from day 1 to day 14.

• **Correlation Analysis**: Spearman's rank correlation coefficient will evaluate associations between imaging metrics (e.g., DTI metrics and PS values) and clinical outcomes, such as NIHSS scores and HT incidence.

8. Safety Analysis

• Adverse Events (AEs): Safety will be assessed by tracking and comparing the incidence of AEs in each group, with specific attention to known Cerebrolysin side effects such as mild agitation and hypotension. Proportions will be compared using χ^2 -tests or Fisher's exact test, as appropriate.

9. Software and Statistical Significance

- Software: STATA v.14.2 and IBM SPSS v.26.
- **Significance Level**: α = 0.05 for primary and secondary endpoints, with multiple hypothesis correction for primary outcomes using Romano-Wolf adjustment.

This Statistical Analysis Plan (SAP) provides a detailed framework for assessing the impact of Cerebrolysin on hemorrhagic transformation, neurological recovery, functional outcomes, and safety in MCA stroke patients undergoing IVT. The exploratory imaging analysis aims to substantiate Cerebrolysin's neuroprotective role by examining advanced imaging biomarkers of blood-brain barrier stability and infarct recovery. This SAP is essential for ensuring that the study findings are robust, reproducible, and clinically meaningful.

II. Statistical Analysis Plan for Post Hoc Analysis of the CEREHETIS Trial (Heterogeneous Treatment Effect Analysis)

1. Introduction

The post hoc analysis of the CEREHETIS trial aims to evaluate the heterogeneous treatment effects (HTE) of Cerebrolysin as an early add-on to intravenous thrombolysis (IVT) in MCA stroke patients. Given the variability in hemorrhagic transformation (HT) risk, this analysis seeks to identify subgroups of patients who benefit most from Cerebrolysin by stratifying them according to HT risk at admission. Multiple predictive scores, including the DRAGON, SEDAN, and Hemorrhagic Transformation Index (HTI), will be used for this purpose. The primary endpoints include any and symptomatic HT and functional outcome at day 90, defined by the modified Rankin Scale (mRS).

2. Objectives and Endpoints

- **Primary Objective**: To evaluate the heterogeneous treatment effects (HTE) of Cerebrolysin on hemorrhagic transformation (HT) and functional outcomes based on HT risk levels.
- Primary Endpoints:
 - Any HT and Symptomatic HT rates within 14 days.
 - **Functional Outcome**: Modified Rankin Scale (mRS) score on day 90, with favorable functional outcome (FFO) defined as mRS \leq 2.

• Secondary Endpoints:

- Subgroup-specific treatment effects on symptomatic and any HT, as well as FFO, across risk levels determined by DRAGON, SEDAN, and HTI scores.
- Evaluation of Cerebrolysin's effect on different levels of HT risk to guide potential stratification in future clinical practice.

3. Statistical Analysis

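### The 80% power in SAP Section I.4 is for one HT rate at 0.05 with no multiplicity allowance shown, although two primary HT outcomes are tested under Romano-Wolf correction

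*SAP*

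**What the plan says.** **Sample size (SAP Section I.4).** The power statement concerns one primary endpoint, labelled as the HT rate: "Based on the assumption that 20% of control group patients will experience HT, with a target odds ratio (OR) of 0.5" for Cerebrolysin. The other inputs are "Significance Level: 0.05", power 80% and dropout 10%. The section gives no total N, no sidedness, no rate for symptomatic HT and no mention of multiple testing.

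**Primary outcomes (Sections I.1, I.2, I.7b).** The introduction says: "The primary outcome focuses on the rate of any HT and symptomatic HT within 14 days post-intervention". The primary objective repeats both outcomes, and the primary analysis compares both between arms by logistic regression.

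**Multiplicity (Section I.9).** The level is 0.05, "with multiple hypothesis correction for primary outcomes using Romano-Wolf adjustment".

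The SAP sets no testing order and names neither outcome as the only one powered. It does not say whether success means one outcome or both.

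**The concern.** The power statement and the planned test do not describe the same thing. Section I.4 describes one comparison at 0.05. The analysis makes two comparisons, and each must pass a threshold adjusted for the other.

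Two consequences follow. First, if no allowance for the correction was built in, any HT has less than the stated 80%. Second, symptomatic HT is a subset of any HT, so one 20% control rate fits both only if every haemorrhage is symptomatic. With the unqualified term read as any HT, symptomatic HT has a lower rate and no stated power.

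What is at stake is how a non-significant result is read. Without a qualification, a null finding on symptomatic HT could be taken as evidence from a primary endpoint with 80% power. Sections II and III again list both HT outcomes as primary, so the ambiguity can carry into later reports.

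**Working it through.** **Inputs from the SAP.** Control rate p1 = 0.20, OR 0.5, level 0.05, power 80%, dropout 10% (all Section I.4). Section I.3 gives control:Cerebrolysin as 1:2 ("Patients are randomized in a 1:2 ratio to receive either IVT alone or IVT with Cerebrolysin"). Section I.4 words the ratio the other way round, so both directions were run.

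**Assumptions, not in the SAP.** Two-sided test; unqualified HT means any HT; symptomatic HT control rate varied from 2% to 15%; symptomatic OR 0.5, then 0.33 and 0.2.

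**Step 1: Cerebrolysin rate.** Odds = 0.5 × 0.20/0.80 = 0.125, so p2 = 0.125/1.125 = 0.111 and the difference is 0.0889.

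**Step 2: the N that the stated inputs imply.** There is no stated N to reproduce, so it has to be derived. With control fraction f and p̄ = f·p1 + (1−f)·p2:

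N = {[1.96·√(p̄(1−p̄)(1/f + 1/(1−f))) + 0.842·√(p1(1−p1)/f + p2(1−p2)/(1−f))] / (p1−p2)}²

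- f = 1/3: p̄ = 0.1407; (1.446 + 0.667)/0.0889 = 23.77; squared, about 565.
- f = 2/3: p̄ = 0.1704; (1.563 + 0.616)/0.0889 = 24.52; squared, about 601.

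Rounded up to whole arms these are 567 (189 + 378) and 602 (401 + 201). With dropout they are 567/0.9 = 630 and 602/0.9 = 669. Power for one HT rate at 0.05 is then 80%, by construction.

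**Step 3: lower bound under correction.** With each outcome tested at 0.025 (Bonferroni), power for any HT is 72% at N = 567 and 70% at N = 602. Restoring 80% at 0.025 would take 684 or 732 evaluable patients.

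**Step 4: step-down max-|Z| correction.** Romano-Wolf uses the correlation between the outcomes and so costs less than Bonferroni. It was approximated by simulating 200,000 trials per scenario, with symptomatic HT nested in any HT. At symptomatic rates of 2–6% the first-step level is about 0.026–0.027. Results at N = 567 / 602, symptomatic OR 0.5:

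| Assumed symptomatic control rate | Any HT | Symptomatic HT | At least one | Both |
|---|---|---|---|---|
| 3% | 74% / 72% | 22% / 15% | 75% / 72% | 21% / 15% |
| 5% | 74% / 73% | 33% / 26% | 76% / 74% | 31% / 25% |
| 8% | 75% / 74% | 46% / 41% | 76% / 75% | 44% / 40% |
| 10% | 76% / 74% | 54% / 49% | 77% / 76% | 52% / 48% |

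Over 2–6%, any HT has about 72–74% and symptomatic HT about 10–38%. At 15%, any HT reaches 76–77% and symptomatic HT about 68%.

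**Step 5: sensitivity to the symptomatic effect.** At a 6% control rate, corrected power for symptomatic HT is about 58–65% at OR 0.33 and 81–85% at OR 0.2. Power for any HT also rises with a stronger symptomatic effect, because rejecting symptomatic HT first relaxes the second step. Across ORs of 0.5 to 0.2 and rates of 2–10% it runs from 72% to 80%.

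**Step 6: other sizing conventions.** Designs sized for 80% without a continuity correction (one- or two-sided, either allocation, or 1:1) fall to 69–72% at 0.025. Those sized with one start at 83–84% and fall to 74–76%.

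**The case against.** A reader might infer that the design fails to deliver 80% power. The documents do not show that. Power depends on N, and the SAP states none. The 0.05 in Section I.4 could be the familywise level, since Section I.9 also writes 0.05 and then adds the correction. Only an N could settle this: about 567 evaluable points to unadjusted sizing, about 684 to sizing at 0.025. A larger enrolled N would offset the loss on any HT. This objection stands, and it makes the shortfall conditional.

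A reader might also take a narrow band such as 10–38% as the power for symptomatic HT. That band holds only for assumed rates of 2–6% with OR 0.5, and Section I.4 extends neither its rate nor its OR to symptomatic HT. Stronger effects raise the power well above the band. At a 6% rate with OR 0.33 and one third control, power to succeed on at least one outcome is 83%. This also stands: the figures are illustrations and must not enter the plan as facts.

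Finally, the SAP never claims 80% for symptomatic HT, the planned 95% confidence intervals will show imprecision directly, and the trial calls itself a pilot. These points lower the severity. They do not remove the mismatch: Section I.4 does not say that its 80% is for any HT tested alone, and any HT will still be judged at the corrected threshold. Covariate adjustment might recover some power, but the SAP takes no credit for it.

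**Conclusion.** The concern holds in conditional form. Section I.4 shows no multiplicity allowance, and its single 20% rate cannot describe both nested outcomes unless they coincide.

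- **Any HT.** If the trial was sized from the stated inputs at an unadjusted two-sided 0.05, corrected power is about 72–74% for assumed symptomatic rates of 2–6% at OR 0.5. That is a loss of roughly 6–8 points. It shrinks to 3–4 points at a 15% rate and nearly vanishes only if the symptomatic effect is much stronger than OR 0.5.
- **Symptomatic HT.** The stated 80% does not cover it. At OR 0.5 its corrected power is about 10–54% over assumed control rates of 2–10%, and higher for stronger effects.

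This is an inconsistency in the design justification. With no total stated, there is no arithmetic result in the plan to be wrong. Type I error is controlled and no estimate or interval changes, so the point should be corrected but is not a must-fix.

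**What to change.** Reword Section I.4 to do four things:

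1. State that 80% power applies only to any HT, tested alone at two-sided 0.05.
2. Give the actual N and report the power for any HT at that N under the Romano-Wolf correction, with the assumed symptomatic rate and OR stated. If the trial was sized from the present inputs, this will be about 72–74% at symptomatic rates of 2–6% and OR 0.5.
3. State that symptomatic HT was not powered, and show its power over a stated range of control rates and odds ratios, labelled as assumptions.
4. Say that a non-significant symptomatic HT result is inconclusive and is not evidence of no effect.

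The cost is SAP wording and one power calculation. No data, test or estimate changes. The drawback is a less favourable stated power.

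### Symptomatic HT, a primary outcome, gets the same adjusted logistic model as any HT with no sparse-data method; Firth regression would be a cheap improvement

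*SAP*

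**What the plan says.** SAP Part I section 1 makes both outcomes primary: "The primary outcome focuses on the rate of any HT and symptomatic HT within 14 days post-intervention". Section 7b analyses them with one method: "Logistic regression will compare the rates of any and symptomatic HT between the Cerebrolysin and control groups". The next bullet of 7b gives the adjustment: "Age, NIHSS, ASPECTS score, and baseline variables such as history of hypertension and previous stroke will be included in multivariate models". That is five named covariates plus treatment, so at least six terms, and the wording leaves the list open.

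Section 4 sizes the trial on HT as a whole: "Based on the assumption that 20% of control group patients will experience HT, with a target odds ratio (OR) of 0.5 in the Cerebrolysin group". It adds a significance level of 0.05, 80% power and 10% dropout, but gives no resulting N and no rate for symptomatic HT. Section 9 corrects the primary outcomes by Romano-Wolf. Fisher's exact test is allowed in section 8, for adverse events only. Part I names no method for sparse or separated data in the HT models.

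**The concern.** Symptomatic HT is a subset of any HT, so it has fewer events, yet it carries the same number of model terms. With few events, one level of a binary covariate, or a whole arm, may contain none. Maximum likelihood then has no finite solution for that coefficient. The analyst must drop the covariate, drop its patients or change method after seeing the outcome, in a trial that is open-label. Without separation, few events per term still make the treatment log odds ratio more variable than it needs to be. Romano-Wolf adds to this if it is run by resampling patients and refitting, because resamples of sparse data have empty cells more often than the original data.

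**Working it through.** **1. Evaluable N.** The SAP gives no N to reproduce, so it is derived from section 4. Control rate 0.20 and OR 0.5 give odds 0.5 × 0.25 = 0.125 on Cerebrolysin, so the rate is 0.125/1.125 = 0.111. With k = Cerebrolysin/control and p̄ = (p_c + k·p_t)/(1 + k):

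n_c = [1.96·√(p̄(1−p̄)(1+1/k)) + 0.842·√(p_c(1−p_c) + p_t(1−p_t)/k)]² / (p_c − p_t)²

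Two-sided testing is assumed. The allocation direction is stated in two ways. Section 3 says "Patients are randomized in a 1:2 ratio to receive either IVT alone or IVT with Cerebrolysin", while section 4 has a "1:2 allocation ratio between the intervention and control groups". The two need reconciling; both are carried here.

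- Reading A (control 1 : Cerebrolysin 2): 189 + 378 = 567 evaluable; 567/0.9 = 630 randomised.
- Reading B (control 2 : Cerebrolysin 1): 401 + 201 = 602 evaluable; 602/0.9 = 669 randomised.

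One- or two-sided variants, with or without continuity correction, span 450 to 651 evaluable.

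**2. Any HT, for comparison.** Reading A: 189 × 0.20 + 378 × 0.111 = 79.8 events, or 13.3 per term. Reading B: 401 × 0.20 + 201 × 0.111 = 102.5, or 17.1 per term. No separation occurred in simulation, so ordinary logistic regression is adequate for any HT.

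**3. Symptomatic HT.** The control rate is an assumption (2% to 10%; 20% is the ceiling, since it is a subset of any HT), with OR 0.5. Expected events = n_c·p_c + n_t·p_t. At 2%, p_t = 0.0101: reading A gives 3.78 + 3.82 = 7.6 and reading B gives 8.02 + 2.03 = 10.1. P(an arm is empty) = a + b − ab, with a = (1−p_c)^n_c and b = (1−p_t)^n_t. The last column comes from 500 simulated trials per setting, with separation detected by linear programming. The model had treatment, three continuous covariates and two binary ones (hypertension 70%, previous stroke 15%); these covariate inputs are assumptions. Entries are reading A / reading B.

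| Control rate | Events | Events per term (6) | An arm empty | Any coefficient non-finite |
|---|---|---|---|---|
| 2% | 7.6 / 10.1 | 1.3 / 1.7 | 4.3% / 13.0% | 42% / 34% |
| 3% | 11.4 / 15.1 | 1.9 / 2.5 | 0.6% / 4.6% | 21% / 14% |
| 5% | 19.1 / 25.2 | 3.2 / 4.2 | 0.01% / 0.5% | 5.6% / 2.8% |
| 7% | 26.9 / 35.4 | 4.5 / 5.9 | <0.1% / 0.06% | 1.4% / 0% |
| 10% | 38.8 / 50.7 | 6.5 / 8.5 | ~0 / ~0 | 0.4% / 0% |

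The Monte Carlo error at 42% is √(0.42 × 0.58/500) ≈ 2 percentage points. Further simulations with other covariate assumptions widen the last column to about 24-42%, 12-21%, 1-7% and 0-2% at 2%, 3%, 5% and 7% or above. One set-up with 540 to 600 patients and 80% prevalence for one binary covariate reached 27% at 3%.

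**4. Which coefficient fails.** If no event occurs among, say, patients with previous stroke, that covariate's coefficient diverges. Those patients then stop contributing to the likelihood, and the treatment estimate has a finite limit equal to the one from the remaining patients. The treatment OR is lost mainly when an arm is empty. Across the simulations this was about 3-14% at 2%, 0.4-5% at 3%, 0-1% at 5%, and none at 8%. When the OR was finite, maximum-likelihood coverage was 94-99%.

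**5. Firth on the same data.** Estimates were finite in every run checked (60 in each of 14 settings). In trials where maximum likelihood was also finite, Firth cut the root mean squared error of the treatment log OR by about 5-20% in every setting. Overall coverage was 94-97%.

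**6. Resampling.** With 2 events in an arm, a bootstrap resample has none with probability about e⁻² = 13.5%; with 4 events, e⁻⁴ = 1.8%. In simulated trials with no empty arm or covariate level in the original data, an arm was empty in 11-17% of resamples at 2%, 4-10% at 3%, 0.3-3% at 5% and at most 0.9% at 7%.

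**The case against.** A reader might infer that the primary model will fail to give finite estimates. The documents do not support that, for four reasons, all of which stand.

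- **Few events is not stated.** The SAP gives no symptomatic HT rate. At 7-10% there would be 27 to 51 events and almost no failures.
- **Maximum likelihood is not named.** It is only the default reading of logistic regression.
- **The adjusted model is not called primary.** The sentence on comparing rates has no covariates; they come in the next bullet. An unadjusted comparison fails only if an arm is empty.
- **The large percentages mostly concern covariates.** The treatment OR usually survives with acceptable coverage.

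A reader might also extend the point to the score-adjusted models in Part II section 3.2. Those adjust for risk scores, singly or together, which is two to four terms including treatment if each score enters as one term. They have no sparse binary covariate, and that model was not tested, so the extension is not made.

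Finally, Firth is one choice among several, and a fallback rule would also close the gap. That is fair. The case for using Firth outright is that it needs no decision after the data are seen and had smaller error even where maximum likelihood worked.

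**Conclusion.** The point holds as a cheap improvement, at the level of something to consider. A primary outcome that may be sparse is given a model of at least six terms with no sparse-data method. Loss of the treatment OR is a material risk only if the control symptomatic rate is about 2-3%, and it is negligible from 5% upward. The more general gain is the 5-20% lower error and the removal of an unplanned choice about covariates.

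This rests on the derived N, an assumed symptomatic rate of 2-10%, OR 0.5 for symptomatic HT, assumed covariate effects and prevalences, and estimation by maximum likelihood. The resampling figures also assume that Romano-Wolf is run by bootstrapping patients and refitting the model.

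**What to change.** In Part I section 7b, specify Firth penalised-likelihood logistic regression with profile-likelihood confidence intervals for the adjusted symptomatic HT model. In section 9, state that the same fit is used within the Romano-Wolf resamples. Keep ordinary logistic regression for any HT. If results have already been reported, add the Firth fit as a labelled sensitivity analysis instead.

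The cost is a few lines of SAP text, one extra routine and slight shrinkage of the OR toward 1. Profile-likelihood intervals were not themselves simulated here; they are proposed because Wald intervals are unreliable when an arm has no events.

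### The Part I tests of NIHSS recovery and day-90 mRS ≤ 2 omit baseline NIHSS and age, which gives up precision and leaves any chance imbalance uncorrected

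*SAP*

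**What the plan says.** All of this is in Part I of the SAP unless noted.

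- **NIHSS (7b, Secondary Analysis).** "The Mann–Whitney U test will compare NIHSS scores between groups at day 1 and day 14". No baseline value or other covariate is named.
- **Binary mRS (same place).** "The mRS scores on day 90 will be assessed using a χ^2 -test for favorable outcomes (mRS ≤ 2". Again no covariate is named.
- **mRS distribution (same place).** "a shift analysis will be conducted to evaluate distributional differences in mRS scores between groups". Neither a model nor covariates are given.
- **Primary HT analysis (7b).** Here there is adjustment: "Age, NIHSS, ASPECTS score, and baseline variables such as history of hypertension and previous stroke will be included in multivariate models". That bullet sits under the primary analysis and is not repeated for the secondary endpoints.
- **Baseline data (section 6).** The day-0 entry reads "Demographic data, NIHSS, CT, DTI baseline imaging".
- **Randomisation (section 5).** "Simple randomization across centers using Bernoulli variates (probability parameter of 0.333". No stratification, blocking or minimisation is described.
- **Error rate (section 9).** Alpha is 0.05 "for primary and secondary endpoints, with multiple hypothesis correction for primary outcomes using Romano-Wolf adjustment", so each secondary test is read at 0.05 without correction.

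Part II, added in 2023 as a post hoc analysis, includes logistic regression of favorable mRS adjusted for the HTI, DRAGON and SEDAN scores (section 3.2) and ordered logistic models of mRS (section 3.5). Its endpoints are HT and mRS. NIHSS at follow-up is not among them.

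**The concern.** The stated objective is recovery, but a day-1 or day-14 NIHSS score on its own measures status. How far a patient has come depends on the day-0 score, which is the same scale measured earlier and is already on file. Leaving it out keeps the between-patient variation in starting severity in the error term, so the test is weaker than the data allow.

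Simple randomisation balances baseline severity only on average. If one arm happens to start with milder strokes, an unadjusted test cannot separate that from a treatment difference in that particular trial. The plan sees value in adjusting the HT comparison for age and NIHSS, yet drops both for the functional and neurological endpoints. At stake are the power of the plan's clinical recovery endpoints and how credible they look if the baseline table shows an imbalance.

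**Working it through.** The SAP gives no power, SD or effect size for NIHSS or mRS, so there is no figure of its own to reproduce. The working below sizes the loss.

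**Inputs.** From the SAP: alpha 0.05 (taken as two-sided), Bernoulli allocation with probability 0.333, the Mann–Whitney test and the chi-square test. Assumed, because the SAP does not give them: the correlation r between baseline and follow-up, and the total N. Sections 3 and 4 word the direction of the 1:2 ratio differently, but the imbalance formula in step 3 is symmetric in the two arms and does not depend on it.

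**1. NIHSS, by formula.** Adjusting a continuous outcome for a baseline covariate multiplies the variance by 1 − r².

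| r | 1 − r² | variance cut | equivalent extra patients, 1/(1 − r²) − 1 |
|---|---|---|---|
| 0.5 | 0.75 | 25% | 33% |
| 0.7 | 0.51 | 49% | 96% |

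In exact terms the cut at r = 0.7 is 49%, with 51% of the variance remaining; the range is therefore 25 to 49%, and the 51% is the upper bound only if read as the variance left.

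Power after adjustment, starting from 60%, is Φ((z₀.₆ + 1.96)/√(1 − r²) − 1.96), with z₀.₆ = 0.253:

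- r = 0.5: 2.213/0.866 − 1.96 = 0.596, so power is 72%.
- r = 0.7: 2.213/0.714 − 1.96 = 1.139, so power is 87%.

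**2. Check by simulation.** The settings were 1,500 trials each, assumed N = 350, Bernoulli(1/3) allocation, skewed NIHSS-like scores and a treatment shift of 0.33 SD on the underlying scale.

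| r | Mann–Whitney | rank ANCOVA on baseline | chi-square, binary outcome | logistic with baseline |
|---|---|---|---|---|
| 0.4 | 81% | 87% | 61% | 64% |
| 0.6 | 80% | 93% | 62% | 72% |
| 0.8 | 79% | 99% | 59% | 84% |

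The formula started from 80% gives 86%, 94% and over 99% for the same three correlations, so it describes the rank tests well. It does not describe the binary outcome, where the gain at r = 0.4 is about 3 points.

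**3. Chance imbalance.** The baseline difference has standard deviation √(1/n₁ + 1/n₂) in SD units.

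| assumed N | split | SD of difference | chance of exceeding 0.2 SD |
|---|---|---|---|
| 300 | 200/100 | 0.122 | 10% |
| 350 | 233/117 | 0.113 | 8% |
| 600 | 400/200 | 0.087 | 2% |

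An imbalance of 0.2 SD moves the unadjusted comparison by 0.2r, which is 0.10 to 0.14 SD at r = 0.5 to 0.7.

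**4. Type I error.** With no treatment effect, the simulated Mann–Whitney test rejected in 5.0%, 3.9% and 4.6% of trials at r = 0.4, 0.6 and 0.8, which is nominal. Among trials with an imbalance above 0.2 SD it rejected in about 10%, 12% and 34%. Those last figures rest on roughly 110 trials each and are only indicative.

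**The case against.** The strongest reply is that nothing here is invalid. Under randomisation both tests hold their level, and the chance baseline difference is ordinary sampling variation that the test already allows for. That stands. A reader might infer that the unadjusted tests are biased or inflate alpha; step 4 shows that overall they do not. The excess appears only conditional on a sizeable imbalance, which is uncommon: 2 to 10% of trials over the assumed sizes.

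Second, the 1 − r² factor belongs to continuous outcomes. A reader might carry the equivalent of 33 to 96% more patients over to mRS ≤ 2. The simulation does not support that.

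Third, the mRS shift analysis might be cited as another unadjusted test. The SAP names no model for it, so it is under-specified. It can be counted neither as unadjusted nor as an answer to the point.

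Fourth, Part II already adjusts mRS ≤ 2, and DRAGON contains age, NIHSS and pre-stroke mRS. This weakens the mRS half of the point. It does not remove it, because that analysis is post hoc, works through composite scores and leaves NIHSS recovery untouched.

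Finally, these are secondary endpoints of a pilot study, which limits the consequence. Skewed scores are no reason to avoid adjustment, since rank ANCOVA and proportional-odds models do not require normality.

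**Conclusion.** The point holds as one of efficiency and of unprotected chance imbalance, not of bias. It is strongest for NIHSS, where the omitted covariate is the same scale at day 0. At an assumed correlation of 0.5 to 0.7, adjustment leaves 75% down to 51% of the variance and raises 60% power to about 72 to 87%. For mRS ≤ 2 the gain is smaller, about 3 points at r = 0.4 and 10 points at r = 0.6 in simulation at an assumed N of 350.

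The correlation and N are both assumptions. At a correlation of 0.4 the NIHSS gain is modest (81 to 87% in simulation); at 0.6 or above it is large. The change should be made, but the planned tests would not produce a wrong answer on average.

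**What to change.** In Part I, section 7b:

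- **NIHSS at day 1 and day 14:** make the main secondary analysis a proportional-odds model or rank ANCOVA on treatment, baseline NIHSS and age. Choose one and name it.
- **mRS ≤ 2 at day 90:** use logistic regression on treatment, age and baseline NIHSS.
- **mRS shift:** name ordinal logistic regression with the same covariates.
- **Pre-stroke mRS:** add it to both mRS models if it was recorded for all patients. Its use in DRAGON in Part II suggests so, but the Part I day-0 list does not mention it.
- **Unadjusted tests:** keep the Mann–Whitney and chi-square tests as supportive.

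The covariate list should be closed, with no open-ended examples. The cost is SAP wording, with no new data beyond what is collected. The SAP ties its issue date to the trial's original report, so results may already be known. If they are, the adjusted analyses should be labelled as added later and reported beside the planned ones.
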